2.3.2 Known Potential Benefits

There are no definitive currently known benefits of encaleret in the target population of PSH. However, this proof-of-principle study could possibly identify a novel therapeutic class for PSH, one which might allow patients with PSH maintain eucalcemia without increasing the risk of renal calcification. This study may possibly identify the PTH-independent effect of CaSR on renal calcium reabsorption, thereby contributing the greater body of knowledge and could inspire future therapeutic studies.

2.3.3 Assessment of Potential Risks and Benefits

This study is designed to minimize known potential risks (as described above) while allowing for the examination of the PTH-independent effect of CaSR on renal calcium reabsorption. This study will also address, in a proof-of-principle manner, the potential utility of encaleret as a therapy in patients with postsurgical hypoparathyroidism.

The primary known risk to patients of being enrolled in this study is the risk of hypercalcemia or hypocalcemia. To mitigate these risks, the study is entirely inpatient, calcium will be closely monitored, and supplementation will be adjusted as required. An algorithm for response to hyper/hypocalcemia is detailed in Table D including stopping criteria for Encaleret.

The risks of participation are reasonable relative to the medical knowledge that may be achieved.

3 OBJECTIVES AND ENDPOINTS

OBJECTIVES	ENDPOINTS	JUSTIFICATION FOR ENDPOINTS
Primary		
Evaluate the PTH-independent effects of encaleret on renal calcium	Percent change in Fractional Excretion of Calcium (FECa) from baseline (Day -1) to the final day	FECa reflects the relationship between blood calcium and

OBJECTIVES	ENDPOINTS	JUSTIFICATION FOR ENDPOINTS
handling in participants with PSH.	of treatment (Day 6 or the last measurement while on encaleret). FECa calculated using fasting blood levels and spot urine collections.	urinary calcium. CaSR modulation by encaleret is expected to directly affect FECa. If a patient stops encaleret early prior to Day 6, the last fasting FECa on encaleret 162 mg BID will be used for this endpoint.
Secondary		
Evaluate the ability of encaleret to normalize blood calcium while maintaining a normal urinary calcium in participants with PSH.	Proportion of participants who achieve a concomitant normal or elevated fasting blood calcium (albumin-corrected calcium >8.5 mg/dL) and a normal 24-hour urinary calcium level (<250 mg/24 hours for women, <300 mg/24 hours for men) on encaleret at any point between day 1 and day 5.	Clinically relevant endpoint to determine if encaleret can allow PSH to have both normal blood and urinary calcium.
Tertiary/Exploratory		
Evaluate the ability of encaleret to increase serum iPTH levels in participants with PSH.	Change in blood iPTH comparing average baseline iPTH to average peak iPTH on encaleret. The average baseline iPTH will include all baseline iPTH levels from the screening visit, Day -1, and pre-dose on Day 1. The average peak iPTH will average the peak iPTH levels on every day the patient is on encaleret (days 1 to 5). An increase in iPTH will be	Averaging iPTH will prevent spurious excursions from impacting outcomes

OBJECTIVES	ENDPOINTS	JUSTIFICATION FOR ENDPOINTS
	considered clinically significant if there is an increase both by 50% AND by more than 10 pg/dL.	
Evaluate the effect of encaleret on 1-alpha hydroxylase action by measuring 1,25-(OH) ₂ Vitamin D levels.	Change in 1,25-(OH) ₂ Vitamin D on encaleret comparing the maximal level prior to receiving calcitriol (On Days 3-5) to baseline (Average of Day 1 Pre-dose levels). Increase will be considered significant if there is an increase of more than 50%. Participants who receive calcitriol prior to Day 3 will be excluded.	

Explore the dynamic effect of encaleret on blood and urinary calcium and citrate, iPTH, cAMP, and 1,25-(OH)₂ Vitamin D.
 
Evaluate the effect of encaleret on bone turnover in participants with PSH.
 
Evaluate the effect of encaleret on phosphate, magnesium, and FGF23 levels.
	
Percent change in Fractional Excretion of Calcium (FECa) from baseline (Screening visit) to the final day of treatment (Day 6 or the last measurement while on encaleret). FECa calculated using fasting blood levels and spot urine collection.
 
Pharmacodynamic endpoints measured over time over 5 days of encaleret therapy:
 
 • Blood iPTH – Absolute levels and change from baseline • Albumin-corrected blood calcium - Absolute levels and change from baseline in cCa • Ionized Calcium – Absolute levels and change from baseline • Urinary calcium clearance (fractional excretion and 24- 	These endpoints will allow us to further explore the effect of encaleret on other markers of bone and mineral metabolism and identify areas for future study.

OBJECTIVES	ENDPOINTS	JUSTIFICATION FOR ENDPOINTS

Explore the effects of encaleret on 24-hour urine markers that impact stone formation
	
hour total excretion) - Absolute levels and change from baseline
 
 • Serum levels of 1,25-(OH)₂ Vitamin D - Absolute levels and change from baseline • Blood iFGF23 and cFGF23 - Absolute levels and change from baseline • Urine cAMP and citrate - Absolute levels and change from baseline • Bone resorption markers collagen cross-linked C-telopeptide (CTX) - Absolute levels and change from baseline • Bone formation markers – blood procollagen type 1 N-propeptide (P1NP) - Absolute levels and change from baseline • Change in components of urine including: supersaturation, sodium, potassium, calcium, magnesium, chloride, phosphorus, sulfate, citrate excretion, oxalate, pH, uric acid, creatinine, osmolality, ammonium, urea nitrogen, protein catabolic rate 	

 • Examine the PK of encaleret in participants with PSH and explore PK-PD interactions. 	
 • PK parameters such as maximum plasma concentration (C_{max}), time to maximum plasma concentration (t_{max}), apparent terminal half-life (t_{1/2}) 	

OBJECTIVES	ENDPOINTS	JUSTIFICATION FOR ENDPOINTS

Explore the effect of encaleret on bone and mineral homeostasis in the following sub-groups, as defined in Section 9.3
 
Populations for analysis:
 
• Permanent hypoparathyroid (Cohort 1)• Recent Hypoparathyroid (Cohort 2)• “PTH-Clamp” population• “Aparathyroid” population• Hyperthyroid cohort• Normothyroid cohort• Thyroid cancer cohort	
• Subgroup analysis of other primary, secondary, and tertiary endpoints	
Primary analysis of all endpoints will be performed on the entire population, but subgroup analysis will also be performed for exploratory and hypothesis-generating purposes.

4 STUDY DESIGN

4.1 Overall Design

This will be a single-site, open-label, phase 2, proof-of-principle study to evaluate the PTH-independent effects of encaleret on renal calcium handling in participants with hypocalcemia due to PSH.

Up to 30 participants may be enrolled to support up to 15 participants entering the treatment phase of the study. Two main cohorts are planned:

Cohort 1: Permanent PSH with neck surgery ≥ 12 months ago (minimum 7, up to 10 participants)

Cohort 2: Recent PSH with neck surgery < 12 months ago (up to 5 participants)

4.2 Scientific Rationale for Study Design

The current clinical trial is a small proof-of-principle trial designed to explore PTH-independent effects of encaleret on calcium homeostasis and to determine the ability of a calcilytic to decrease urinary calcium excretion and raise blood calcium in patients with PSH. Encaleret has the potential to fill the unmet need of an oral medication for PSH that can maintain eucalcemia without increasing the risk of hypercalciuria and renal calcifications.

Our primary analyses will include all participants who received at least one dose of the study drug. However, sub-group analysis will also be performed on patients with recent PSH (cohort 2) to explore whether maximal PTH stimulation by a calcilytic can transiently increase PTH secretion in healing parathyroid glands. Patients with recent PSH have the potential to either

have resolution of their hypoparathyroidism or progression to permanent hypoparathyroidism. They will likely respond to encaleret at the kidney level very similarly to cohort 1 in terms of the primary endpoint, FECa, because their kidneys presumably function the same. However, since these patients may have reversible parathyroid gland damage, they may be more likely to increase PTH secretion in response to maximal stimulation by encaleret. It should be noted that the dose of encaleret that is being used will be biologically sensed as profound hypocalcemia to a degree that would never be experienced by a patient with PSH and as such may function as a much more potent stimulator of PTH secretion.

Furthermore, because patients with PSH have variable residual parathyroid tissue, we will also perform exploratory sub-group analyses on a “PTH-Clamp” population whose iPTH did not increase more than 10 pg/mL on encaleret and a “Aparathyroid” population whose absolute iPTH level was less than 10 pg/dl throughout the study. The biochemical response of these subpopulations will likely more accurately reflect PTH-independent effects of CaSR modulation.

4.3 Justification for Dose

The current study proposes to initiate first-in-patient dosing in the new target population of participants with PSH with encaleret 162 mg BID over a 5-day inpatient admission.

Twice a day dosing is necessary to maximize and sustain the effect on renal calcium excretion. In previous studies in euparathyroid patients, once daily dosing did not normalize 24-hour urinary calcium excretion, however, calcium excretion was suppressed for the first 12 hours. In the ongoing Phase 2B study of patients with ADH1 due to activating CASR mutations, encaleret needed to be given twice daily to maintain 24-hour effects on blood and urine calcium.

The present PSH cohort is expected to be protected from hypercalcemia experienced by previous cohorts on encaleret (normal controls or patients with osteoporosis or ADH1). This is because patients with PSH, who have insufficient parathyroid tissue, are unlikely to have a robust PTH response to encaleret. On the other hand, because of the lack of functional parathyroids in this patient population, these patients may be at increased risk of symptomatic hypocalcemia during the course of the study. Thus, maximizing the encaleret dose in this population is both important for the safety of the patients, to reduce risk of hypocalcemia, as well as increasing the probability of establishing a definitive proof-of-principle which is the goal of this study.

A primary concern in this proof-of-principle study is to not make a type 2 error (not see an effect when one exists). Thus, we chose the highest dose that has been safely used previously in patients with hypoparathyroidism/ADH1 to increase the likelihood that we will see our predicted effect.

5 STUDY POPULATION

5.1 Inclusion Criteria

Participants must meet the following criteria for inclusion during screening:

1. Be able to understand and sign a written informed consent form, which must be obtained prior to initiation of study procedures.

2. Age \geq 18 years
3. Postmenopausal women are allowed to participate in this study:
 - a. Women are considered postmenopausal and not of childbearing potential if they have had 12 months of natural (spontaneous) amenorrhea with an appropriate clinical profile (e.g., age appropriate, history of vasomotor symptoms) or have had surgical bilateral oophorectomy (with or without hysterectomy) or tubal ligation at least 6 weeks prior to start of the study. In the case of oophorectomy alone, only when the reproductive status of the woman has been confirmed by follow up hormone level assessment, shall she be considered not of childbearing potential.
4. Body mass index (BMI) \geq 18.5 to $<$ 39 kg/m²
5. Have a diagnosis of PSH, either permanent PSH (Cohort 1, surgery \geq 12 months ago) or recent PSH (Cohort 2, surgery $<$ 12 months ago).
6. Participants must have achieved an albumin-corrected blood calcium level of 7.8-10.2 mg/dL on conventional therapy without significant symptoms of hypocalcemia or hypercalcemia.
7. Participants being treated with thiazide diuretics may be enrolled if they are willing and able to discontinue thiazides for at least 5 half-lives prior to initiation of encaleret and remain off during the study treatment period. (5 half-lives of hydrochlorothiazide = 75 hours; chlorothiazide = 10 hours; chlorthalidone = 12.5 days). If the thiazide is being used as an antihypertensive, as opposed to use as a urine calcium-lowering drug, alternative therapy will be offered.
8. Participants being treated with strong CYP3A4 inhibitors (including clarithromycin, telithromycin, nefazodone, itraconazole, ketoconazole, atazanavir, darunavir, indinavir, lopinavir, nelfinavir, ritonavir, saquinavir, tipranavir) may be enrolled if they are willing and able to discontinue these medications for at least 5 half-lives prior to initiation of encaleret and remain off during the study treatment period.
9. Participants being treated with magnesium or potassium citrate supplements should discontinue such treatment starting on Day -2.
10. Participants being treated with medications that have impacts on mineral metabolism which investigators believe may impact study endpoints may be enrolled if they are willing and safely able to discontinue the medication for at least 5 half-lives prior to initiation of encaleret and remain off during the study treatment period

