1.3 Schedule of Activities (SOA)

Table A Schedule of Activities

	Screening	NIH CC Inpatient Treatment Visit							Discharge	FU Lab ⁷	Lab Phone FU ⁸	30- Day Phone FU ⁹	90-Day Phone FU ¹⁰
		Admission		BID Dosing									
Days	-180 to -2	-2 OR -1	-1	1	2	3	4	5	6	8-12	9-15	30 ± 7	90 ± 7
Informed Consent	X												
Admission to clinic/ inpatient floor ¹	X	X											
Demographi cs, Medical history	X												
Eligibility assessment	X												
Height	X												
Weight	X		X					X					
Vital signs ²	X		X	X	X	X	X	X	X				
Physical examination	X		X					X					
Aes and SAEs, Prior/ Concomitant meds	X	X	X	X	X	X	X	X	X	X	X	X	
NPO at midnight for morning fasting labs; water and medications ok			X	X	X	X	X	X	X				
Encaleret 162 mg q12h				X	X	X	X	X					
Calcium Carbonate, individualize d dosages			X	X	X	X	X	X					
Nutritionist Visit	X												
Quantify dietary calcium intake			X	X	X	X	X	X					

Stop magnesium and potassium citrate (last doses on day -3)		X	X										
Stop activated vitamin D and baseline calcium supplements (last doses on day -2) ³			X										
Start calcitriol if cCa < 8.5 mg/dL ³						X	X	X					
Discharge, resume conventional therapy									X				
Telephone Contact											X	X	X
Screening Lab Tests ⁴	X												
Safety laboratory testing ⁵										X			
Evening mineral panel (Ca, Mg, PO ₄ , albumin)			X										
Blood β-HCG pregnancy test (WOCBP only)	X		X							X			
Blood Sampling ⁶			X	X	X	X	X	X					
24-hour Urine (Ca, Mg, PO ₄ , Cr, Na, K, Citrate, pH)	X		X	X	X	X	X	X					
Timed interval urine collections ⁷				X	X	X	X	X					
Renal Ultrasound	X												
ECG, 12-lead	X		X	X	X	X	X	X					

Abbreviations: Adverse Event = AE; Albumin = Alb; Electrocardiogram = ECG; BID = Twice daily; Blood Pressure = BP; Calcium = Ca; Chloride = Cl; Concomitant Medication = Con. Meds; Creatinine = Cr; Early Termination = (ET); End of Treatment = EoT.

Follow-up = FU; Heart Rate = HR; Lactate Dehydrogenase = LDH; Intact Parathyroid Hormone = iPTH; Magnesium = Mg; NPO = Nothing by mouth; National Institute of Health Clinical Center = NIH CC; Parathyroid Hormone = PTH; Phosphate = PO₄; Phosphorus = P; Potassium = K; Prothrombin Time/ Prothrombin Time = PT/INR; Red Blood Cell Count = RBC; Thromboplastin Time = PTT; Serious Adverse Event = SAE; Women of Childbearing Potential = WOCBP

¹ Participants may complete the Screening Visit as outpatients or be housed overnight at NIH CC.

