 - History of clinically significant cardiac arrhythmias including ventricular arrhythmias, atrial fibrillation, or conduction abnormalities
 - History of unstable angina pectoris or acute myocardial infarction
11. Participants with positive hepatitis B surface antigen (HBsAg) or Hepatitis A immunoglobulin M (IgM) at the Screening Visit. Participants who are in complete remission from Hepatitis C as evidence by sensitive assay \geq 12 weeks after completion of HCV therapy are allowed to participate in the study. Participants with human immunodeficiency virus (HIV) infection on a stable dose of anti-retroviral therapy who have an undetectable viral load are allowed to participate in the study.

12. Pregnant or nursing (lactating) women, where pregnancy is defined as the state of a female after conception and until the termination of gestation, confirmed by a positive serum hCG laboratory test
13. Clinically significant abnormalities in thyroid function tests. This does not include participants with non-clinically significant or treated thyroid diseases (e.g. subclinical hypothyroidism, hypothyroidism on treatment, etc). Participants on TSH-suppression therapy for thyroid cancer are allowed to participate in this study regardless of TSH level.
14. Women of child-bearing potential, defined as all women physiologically capable of becoming pregnant, unless they are using highly effective methods of contraception during dosing and for 3 months following the discontinuation of study treatment. Highly effective contraception methods include:
 - Total abstinence (when this is in line with the preferred and usual lifestyle of the subject). Periodic abstinence (e.g., calendar, ovulation, symptothermal, post-ovulation methods) and withdrawal are not acceptable methods of contraception.
 - Female sterilization (have had surgical bilateral oophorectomy with or without hysterectomy) or tubal ligation at least six weeks before taking study treatment. In case of oophorectomy alone, only when the reproductive status of the woman has been confirmed by follow up hormone level assessment.
 - Male sterilization (at least 6 months prior to screening). For female participants on the study the vasectomized male partner should be the sole partner for that subject.
 - Combination of the following (a+c or b+c):

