6.1.2 Dosing and Administration

On Day -1/-2, participants who met eligibility criteria at the screening visit will be admitted to the NIH CC. Participants will not take their magnesium and potassium citrate starting on the morning of Day -2. Participants will not take their standard-of-care calcium or calcitriol starting on the morning of Day -1, and will instead start a personalized calcium supplementation, determined by investigators from their baseline calcium requirements and levels. They will start on a dietary daily calcium intake of approximately 1000 mg per day, which may be adjusted if needed.

Encaleret 162 mg twice a day will be administered to participants on Day 1 to 5. Additional calcium and/or calcitriol will be administered per algorithm (Table D) if required.

Calcium and calcitriol supplementation will be adjusted following the algorithm delineated in Table D with the primary goal of safety. Mild to moderate symptomatic hypocalcemia at any calcium level, cCa < 7 mg/dL, or borderline QT prolongation, would cause investigators to give oral calcium and/or calcitriol. Doses will be determined at the discretion of experienced investigator's understanding of the patient's prior supplement requirements and severity of hypocalcemia. IV calcium may be used for participants with severe hypocalcemic symptoms or QTcF > 500 ms. If a patient develops mild hypercalcemia, then calcium and calcitriol will be held until cCa is less than 9 mg/dL. If cCa has not trended down by 12 hours (or earlier per investigator discretion), encaleret will be stopped. If cCa is > 12 mg/dL, encaleret will be discontinued and calcium and calcitriol will be held until cCa is < 9 mg/dL, when home regimen is restarted.

On Day 3, investigators will add calcitriol supplementation if the albumin-corrected calcium remains < 8.5 mg/dL. The calcitriol dose will be determined by investigators, taking into account the current calcium level and the subject's baseline requirements.

The last dose of encaleret will be given on the night of Day 5. The patient will then resume calcium and calcitriol and be discharged home. If the patient is hypercalcaemic or hypocalcemic, their baseline calcium and calcitriol may be adjusted at discharge. If needed, they may remain at the NIH clinical center until their labs have stabilized to a safe level.

Table D: Titration algorithm:

		Encaleret Titration	Calcium supplementation titration*	Calcitriol titration*	Additional interventions/ monitoring

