7.2 Participant Discontinuation/Withdrawal from the Study

Participants are free to withdraw from participation in the study at any time upon request.

An investigator may discontinue or withdraw a participant from the study for the following reasons:

- AEs

- Protocol violation
- If it is discovered that the subject did not meet protocol entry criteria, and continued participation would present unacceptable risk to subject's health
- Non-compliance with administration of the investigational medicinal product encaleret (IMP)
- Withdrawal of consent: Participants may withdraw consent at any time for any reason without prejudice to future treatment. In the event of study withdrawal, the subject will be encouraged to undergo ET procedures as a final visit.
- Lost to follow-up
- Pregnancy at any time after signing the ICF.
- Study terminated by Sponsor
- Site closed by Sponsor
- PI's decision based on subject's safety

If participants discontinue participation or are terminated early from the study, and have received a dose of encaleret, they should have all follow up safety assessments as listed in the Schedules of Assessments (including one outpatient follow up laboratory assessment and three telephone contacts) if the subject agrees.

When participants are discontinued from study medication, they should be converted back to oral calcium and active Vitamin D. Participants will be instructed to undergo outpatient laboratory testing of their blood calcium within 1 week of discontinuing study medication and to have those results sent to NIH investigators for review. A telephone contact should be arranged for the investigative staff to review the blood results and advise on optimizing their outpatient clinical management.

All dosed participants who early terminate from the study, regardless of cause, should undergo a 30-day (± 7 days) and 90-day (± 7 days) follow-up telephone call after the last dose of encaleret. The reason for early termination from the study will be reflected in the CRF. If a subject early terminates from the study because of an AE, the PI/study staff must record the AE as the reason for subject discontinuation.

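### Sections 5.1 (item 3a) and 5.2 (item 14) classify a premenopausal woman with a tubal ligation differently, and Table A does not say which one decides whether she has a pregnancy test before dosing

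*Combined protocol and SAP*

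**What the plan says.** **Section 5.1, item 3a.** The definition sets two statuses at once: "Women are considered postmenopausal and not of childbearing potential if they have had 12 months of natural (spontaneous) amenorrhea" with a fitting clinical profile, or if they "have had surgical bilateral oophorectomy (with or without hysterectomy) or tubal ligation at least 6 weeks prior to start of the study". The requirement to confirm reproductive status by a hormone level applies to oophorectomy alone, so nothing further is asked of a woman who qualifies through a ligation.

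**Section 5.2, item 14.** WOCBP are excluded unless they use an accepted method of contraception. They are "defined as all women physiologically capable of becoming pregnant". One of the accepted methods is "Female sterilization (have had surgical bilateral oophorectomy with or without hysterectomy) or tubal ligation at least six weeks before taking study treatment".

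**Section 1.3, Table A.** The row "Blood β-HCG pregnancy test (WOCBP only") is marked at Screening, Day -1 and the Day 8-12 follow-up laboratory visit. It carries no reference to item 3a or item 14. Section 2.3.1 likewise ties pregnancy testing to WOCBP status, in the paragraph that names a possible teratogenic effect on the basis of fetal skeletal anomalies in rabbits.

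**Other pregnancy provisions.** Section 5.2 item 12 excludes pregnant women, with pregnancy "confirmed by a positive serum hCG laboratory test", but does not say who must be tested. Section 7.2 lists "Pregnancy at any time after signing the ICF" as a reason for withdrawal, and section 8.3.10 requires dosing to stop at once if a participant becomes pregnant.

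**The concern.** A ligation blocks conception but does not cause menopause. Item 3a nevertheless gives a premenopausal woman with a ligation the postmenopausal label. Item 14 approaches the same operation from the other side, as contraception used by women who can conceive. Since Table A makes the test depend on WOCBP status, the choice of definition decides whether she is tested.

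What is at stake is one safeguard. Exclusion 12, withdrawal under 7.2 and discontinuation under 8.3.10 all cover her, but they can act only on a pregnancy that somebody knows about. The scheduled hCG tests at Screening and Day -1 are the means of finding an unrecognised early pregnancy before exposure. The call at about 90 days that asks about pregnancies comes after it.

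**Working it through.** The documents give no figure to reproduce. The check is a trace of one case through the text, followed by simple counts.

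**Case:** a premenopausal woman with both ovaries and a tubal ligation more than 6 weeks old.

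| Step | If 5.1 item 3a governs | If 5.2 item 14 governs |
|---|---|---|
| Status | Not of childbearing potential; ligation alone suffices | WOCBP on accepted contraception, if she is regarded as able to conceive |
| hCG at Screening | Not scheduled | Scheduled |
| hCG at Day -1 | Not scheduled | Scheduled |
| hCG at Day 8-12 | Not scheduled | Scheduled |
| Pre-dose total | 0 | 1 + 1 = 2 |
| Overall total | 0 | 2 + 1 = 3 |

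**Does the text choose between the columns?** Item 3a states a classification outright and names ligation. Item 14 holds the protocol's explicit definition of WOCBP, the term that Table A uses, but its sterilization bullet lists bilateral oophorectomy beside ligation. Being named in that bullet therefore does not by itself prove that a woman is WOCBP. Neither item refers to the other, and Table A refers to neither. The conflict is not resolved in the documents.

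**Does another procedure close the gap?** The screening laboratory list includes FSH for postmenopausal women. That may inform the investigator about menopausal status, but it is not a pregnancy test, and item 3a does not make the ligation route depend on its result. History and physical examination at screening may reveal a pregnancy, and nothing forbids an unscheduled hCG. None of these is a scheduled pre-dose test.

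**Planned exposure** (section 6.1.2: "Encaleret 162 mg twice a day will be administered to participants on Day 1 to 5"): 5 days × 2 doses = 10 doses; 10 × 162 mg = 1,620 mg.

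**Assays at issue.** Let k be the number of affected treated women. The two readings differ by 3k assays, of which 2k are pre-dose.

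- k = 0: 0 assays
- k = 1: 3 assays, 2 of them pre-dose
- k = 5: 15 assays, 10 of them pre-dose
- k = 15 (every treated participant, a ceiling only): 45 assays, 30 of them pre-dose

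The documents do not give k, so these values are illustrations.

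**Expected harm.** If p is the chance that such a woman is pregnant and unrecognised at dosing, the expected number exposed without a scheduled test is k × p. It lies between 0 (when k = 0) and 15p. The documents give no p. It is assumed small.

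**The case against.** The strongest reply is that item 14 already settles the matter. It is the one place that defines WOCBP, Table A uses that term, and ligation appears there as contraception within the group. On this reading the harm and the missing test cannot coexist: if the woman can conceive, item 14 makes her WOCBP and she is tested; if she cannot, there is nothing to detect. This stands in part. A reader of item 3a and Table A alone might infer that the plan definitely leaves every premenopausal woman with a ligation untested. The documents do not support that, because it requires item 3a to override item 14 and nothing says that it does.

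The reply does not remove the conflict. Staff who apply item 3a as written would record her as not of childbearing potential and omit the test, and they would be following the protocol. The argument from item 14 works only if they set aside an explicit statement in item 3a.

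A second reply is that the sponsor may have meant sterilised women to count as non-childbearing, so that asking for tests is mere preference. That would be a defensible choice, and the documents show no residual risk that refutes it. But then item 14 should not list ligation as a method for WOCBP, and the postmenopausal label would still be wrong for her. The text needs one consistent rule either way.

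A third reply is that the affected number may be zero. That is accepted and sets the weight of the point.

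**Conclusion.** The two eligibility items conflict on the status of a premenopausal woman with a ligation, and the pregnancy-test row inherits the ambiguity. She has 0 or 2 scheduled pre-dose hCG tests according to which item the site follows. This is a minor safety correction, worth making because it is cheap.

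The conclusion rests on the quoted wording and on two assumptions that the documents do not quantify: that some such women may enter treatment, and that their pregnancy risk is small but not nil. A reader might also infer that pregnant women become eligible or that the trial's results are affected. Neither follows. The pregnancy exclusion applies to all women, ligation is accepted under both items, and no endpoint, analysis set or sample size depends on this wording.

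**What to change.** Three steps, of which two change text:

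1. In section 5.1 item 3a, delete the words *or tubal ligation*, leaving the amenorrhea and oophorectomy routes as they are.
2. In section 5.2 item 14, leave tubal ligation as an accepted contraceptive method, with its present timing.
3. In Table A, limit the hCG row to *WOCBP as defined in 5.2 item 14, including women with tubal ligation who do not meet 5.1 item 3a*.

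A woman with a ligation who also meets item 3a through amenorrhea or oophorectomy then needs no test.

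Cost: up to 3 added hCG assays per affected treated woman, and none if the site already tests such women. An affected woman who is screened but not treated would normally add 1, and a rescreen may repeat it. Blood is already drawn at each of these visits. No woman loses eligibility.
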